Statistical Analysis. Responses to the email survey question will be stored in a database. The responses will be tallied and summarized. No formal analyses are planned for survey data. Qualitative data will be extracted from interview summaries and analyzed by [name] (Co-I). Analyses for Aim 2 will employ rapid qualitative analysis strategies to analyze clinician interview summaries. The steps involved in this analysis include: (1) a domain name will be assigned to each question in the interview guide; (2) a summary interview template will be created; (3) the template will be tested and assessed for usability and relevance; (4) after consistency has been established across the summarizers (i.e. the interviewers), the summary template will be completed for all interviews; (5) the content of the summary templates will be transferred into a matrix of domain x respondent, organized by whether the clinician has fit low-gain amplification for tinnitus or not. Steps 1-2 will be completed before interviews commence. Step 3 will occur when the first few interviews have been completed and use of the summary template may be evaluated. Step 4 will continue as interviews occur. Step 5 will complete the rapid data analysis. The matrix produced by step 5 will allow quick perusal of the content of any domain to get a sense of variation in responses and to identify any gaps in the information collected. Additionally, as interview responses are processed, meaningful or powerful quotations will be identified and recorded.

Project Timeline

Table 1. Two-year timeline for study activities, by aim.

Activity	Year 1				Year 2			
	Q1	Q2	Q3	Q4	Q1	Q2	Q3	Q4
Aim 1								
Obtain IRB approval								
Subject Recruitment								
Fitting of hearing aids								
Data collection								
Quantitative analyses								
Qualitative data analysis								
Aim 2	Q1	Q2	Q3	Q4	Q1	Q2	Q3	Q4
Create interview guide								
Assign domain names and draft summary template (steps 1-2 of qualitative analysis)								
Survey Audiology email list								
Select and contact clinicians, schedule interviews								
Interviews								
Test summary template (step 3)								
Complete summary template for all interviews (step 4)								
Complete rapid qualitative analysis (step 5) and write-up								

Study Population

Hearing Aid Study

Approximately 20 participants will be enrolled. To account for potential screen failures, a total of up to 40 candidates will be consented for the study. Participants will be Veterans, recruited from the VA Portland Health Care System (VAPORHCS) and from the surrounding community, and will likely represent the gender and ethnic makeup of Portland and the surrounding area. They can be any gender, any age, any ethnic group, and any race. Special efforts will be undertaken to enroll minorities and women—VA offices that address minority and women's concerns will be contacted directly to inform them about the study. Non-Veterans will be enrolled if necessary to achieve the target number.

Inclusion criteria: Inclusion criteria will include: (1) a score of 5 or greater on section A the Tinnitus and Hearing Survey during the telephone screening; and (2) air conduction hearing thresholds of 25 dB HL or better from .25 kHz through 4 kHz bilaterally as measured at the first study visit; (3) must not be a current hearing aid user; and (4) capable of consenting and participating (including ability to communicate in English).

Exclusion Criteria: Exclusion criteria will include: (1) an air conduction hearing threshold greater than 25 dB HL from .25 kHz through 4 kHz; (2) significant conductive hearing loss—defined as an air-bone gap of 15 dB at more than two frequencies in one ear, or an air-bone gap greater than 20 dB at any one frequency; (3) suspicion of secondary (somatic) tinnitus, or Meniere's disease (either of which can be ruled out with an examination by an appropriate physician); (4) currently a hearing aid user; or (5) any mental, emotional, or health conditions that would preclude full study participation.

VA Clinician Interviews

Approximately 200 VA audiologists will receive the survey email from the study PI. Up to approximately 15 audiologists will be identified from the survey email responses and scheduled for telephone interviews. Lacking any more exact information on the gender and ethnic makeup of VA employees, we expect that representation of women and minorities in our sample will roughly align with US population data. We will collect basic demographic information from all participants. No children will be involved in any part of the study.

Subject Identification/Recruitment

Hearing Aid Study

Recruitment and Screening. Participants will be Veterans recruited from the VA Portland Health Care System (VAPORHCS). Patients with bothersome tinnitus who have been seen for an appointment in the clinic will be identified through the medical record. Whenever possible, existing audiograms will be screened to ensure that candidates with normal hearing through 4 kHz are selected. Alternately, International Classification of Disease, Tenth Edition (ICD-10) diagnosis codes from the medical record will be used to identify those with normal hearing. Letters will be sent to these study candidates. These letters will indicate that candidates may opt out of further contact regarding the study by calling study staff or returning a form. Those who do not opt out may be contacted approximately 2 weeks after receiving the letter. If this does not identify sufficient numbers of potential participants, a broader data pull of Veterans with tinnitus will be collected, and those with diagnosis codes indicating hearing loss will be filtered out. If necessary, we will also pull data for Veterans who have a diagnosis of sensorineural hearing loss to search for candidates who only have hearing loss above 4 kHz.

If these methods fail to identify enough study candidates, participants in past studies at the NCRAR will be used to recruit the remainder needed to fulfill our enrollment goal of 20 participants. These past study participants have indicated their interest and have given permission to be contacted to participate in future research opportunities. Their contact information and basic audiometric test results reside in the NCRAR Subject Data Repository (IRB #2874). Should the need arise, a data use agreement will be signed and approved between the study Principal Investigator (PI) ([name]) and the repository director. Following approval of the Data Use Agreement (DUA), names, contact information and audiometric data will be released from the repository to the study team. Audiometric test results included in the repository will serve to identify candidates who are likely to qualify for the project. Some candidates in the repository are not Veterans, if the data repository is used for recruitment we may recruit non-Veterans. Our primary recruitment focus will be Veterans, however if we are unable to recruit a sufficient number of Veterans we will also recruit civilians.

Identified candidates will be contacted via letter or phone call with information about the research study and will have the opportunity to be telephone-screened to determine if they qualify for participation in the project. Telephone screening will include the Tinnitus and Hearing Survey (THS), which was designed to distinguish tinnitus-specific from hearing-specific complaints²⁹. Items in Section A of the THS include things like trouble concentrating on reading (which would clearly not be rooted in trouble hearing). A minimum score of 5 on the tinnitus portion (Section A) of the THS will be used as the initial qualification of bothersome tinnitus. Having a score of at least 5 will ensure that the person experiences some tinnitus-specific problems that are not hearing-related and that there is room to improve for problems not related to hearing. Candidates screened over the telephone with scores of 5 or more on Section A will be scheduled for the Assessment Visit.

VA Clinician Interviews

Recruitment. Audiologists who choose to participate in the email survey will reply to the Principal Investigator with their responses to the survey questions. From those willing to be

interviewed, approximately 15 audiologists will be selected to complete the telephone interview. Approximately two-thirds of the audiologists interviewed will be those who are conducting the practice, and approximately one-third of the audiologists interviewed be those who are not conducting the practice. Before scheduling the telephone interview, study personnel will confirm that the respondent is in fact a VA clinical audiologist.

Informed Consent & HIPAA Authorization

Hearing Aid Study

Documentation of informed consent will be acquired at the beginning of the first appointment. The candidate will sit in a room (usually sound booth or control room) with a member of the study team to review the information provided in the informed consent form. Once the candidate understands the content of the informed consent form, the candidate may sign the written consent form and a Health Insurance Portability and Accountability (HIPAA) acknowledgement form to indicate their agreement to participate in all study procedures. Testing will begin after informed consent has been documented. Additionally, as part of the informed consent process the subject will have the opportunity to agree to add their data to the Audiology and Rehabilitation Research Data Repository (MIRB #3750, P.I. [name].) for future research and recruitment.

VA Clinician Interviews

An information sheet describing the study along with its risks and benefits will accompany the email survey sent to approximately 200 VA audiologists, via the National Audiology listserv. The information sheet will inform the recipients of the email of the purpose of the study and what will be done with the information received. Anyone who does not consent, need not reply to the email. Clinicians interested in participating will be scheduled for a telephone appointment. At the beginning of the phone call, the interviewer will confirm that the participant received the information sheet and will read a spoken consent script. If the clinician wishes to participate, then an audio-recording will be made of the participant giving spoken acknowledgement of consent to be interviewed and giving spoken consent to be audio-recorded during the interview. After an audio-recording of acknowledgment of consent has been made, then the interview questions (which will be audio-recorded) will begin.

Risks and Side Effects:

Hearing Aid Study

It is possible that faulty equipment might present sounds at too high a level, although this has never happened in the research team's experience over many years of testing, and the equipment and software are typically designed so that such errors would be extraordinarily unlikely. Nonetheless, participants will be encouraged to alert the experimenter if any sound is uncomfortably loud and to feel free to remove or turn off the sound-producing devices at any time if they so wish.

VA Clinician Interviews

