Feasibility and Acceptability of Using Low-Gain Hearing Aids for Bothersome Tinnitus

NCT03904264

March 20, 2019

Research Protocol

Title

Feasibility and Acceptability of Using Low-Gain Hearing Aids for Bothersome Tinnitus

Investigators

Principal Investigator: [name], Au.D.

Specific Aims/Purpose

The study team will obtain pilot data evaluating Veterans with normal hearing thresholds through 4 kilohertz (kHz) and bothersome tinnitus to determine if low-gain hearing aids for tinnitus is an acceptable and feasible approach to addressing bothersome tinnitus, and to provide preliminary data on the impact of providing mild amplification on perceived tinnitus handicap and perceived hearing handicap in the population being studied. This pilot study will also include interviews of clinical audiologists who both are and are not fitting mild amplification for tinnitus on patients with normal hearing. This study is the essential first step toward fully investigating the premise that low-gain hearing aids are effective for individuals who have bothersome tinnitus but who otherwise are not hearing aid candidates.

The project has two Specific Aims.

Aim 1: Measure the reduction in tinnitus handicap when mild amplification through receiver-in-the-canal hearing aids is provided to Veterans with bothersome tinnitus and normal hearing thresholds through 4 kHz.

Aim 2: Document the opinions, procedures, and rationale used clinically to make decisions regarding fitting mild amplification for tinnitus on Veterans with bothersome tinnitus and normal hearing thresholds.

Hypothesis: This pilot study is not hypothesis driven.

Scientific Rationale and Significance

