The use of hearing aids for individuals with bothersome tinnitus and normal hearing is reported by many audiologists to be successful. Audiologists use varying methods to determine the success of the practice, including patient reports of satisfaction, tinnitus outcome instruments, and hearing outcome instruments. However, no systematic study of the feasibility, acceptability, or efficacy of this approach has been conducted. It is essential to show evidence supporting such practice in order to justify the continued use (and expense) of fitting these devices to patients who otherwise do not qualify to receive hearing aids. This is especially important in Veterans whose quality of life suffers from tinnitus, which is the most prevalent service-connected disability¹⁹, and for the Veterans Health Administration. The anecdotal nature of the existing evidence suggests the need for pilot data to determine if a randomized controlled trial (RCT) is warranted and, if so, how to conduct the study. Data from this pilot study will provide critical information regarding recruitment rates of Veterans with normal hearing thresholds through 4 kHz and bothersome tinnitus, compliance and acceptability of the procedures with the target population, and will help to determine if existing tinnitus and hearing outcome instruments are appropriate for use with the target population.

Department of Veterans Affairs (VA) audiologists who have adopted the practice of fitting low-gain hearing aids to Veterans with normal hearing and bothersome tinnitus have each developed procedures for identifying appropriate candidates, fitting the devices, and evaluating outcomes. Their collective experiences comprise a valuable source of data. We therefore plan to survey these audiologists to obtain this information.

Preliminary Studies

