Our team, led by [name] (Co-Investigator on this proposal) has completed two RCTs evaluating combination instruments (hearing aids with a built-in sound generator) for bothersome tinnitus in non-hearing-aid users who were candidates for hearing aids based on their hearing loss^{10, 11}. For both studies, participants used combination instruments either with the sound generator activated or deactivated. For one of the trials, a third group used deep-fit, extended-wear hearing aids¹¹. Outcomes for each study were assessed pre- and post-treatment using the Tinnitus Functional Index (TFI)²⁰. Both RCTs revealed comparable findings: every device studied resulted in decreased tinnitus handicap as measured by the TFI. No significant differences in outcomes were observed between groups.

A caveat should be noted concerning these two RCTs: All participants had both hearing loss and bothersome tinnitus. People will often respond to questions about effects of tinnitus with respect to their hearing loss²¹. For some of the participants, baseline to post-treatment improvement on a tinnitus outcome questionnaire would have resulted from improved hearing. Hearing loss, therefore, confounded the results of these studies, and it is impossible to know how much of the improvement in effects of tinnitus was actually a reduction in hearing difficulties.

This pilot study will specifically look at the use of hearing aids to address bothersome tinnitus in Veteran patients who have hearing within normal limits through 4 kHz based on a conventional audiogram. As already described, such utilization of ear-level devices has anecdotal evidence, but no controlled trials evaluating their efficacy for this purpose. This study will obtain initial data with this population of Veteran patients to determine the feasibility and acceptability of this approach. It is anticipated that results will be positive, which will lead to a

future RCT to fully evaluate such an approach to tinnitus management in this under-served population.

Research Design and Methods

Hearing Aid Study

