Statistical Analysis. All quantitative and qualitative data will be provided to the data manager, who is responsible for developing and maintaining study databases and records. The data manager will perform double entry of the questionnaire data to check for and remediate any errors. The primary goal of Aim 1 will be to provide a preliminary evaluation of benefit of low-gain amplification for all participants. The primary outcome measure for estimating benefit of low gain hearing aids for tinnitus will be the TFI. Secondary outcome measures, including the HHIA and the QuickSIN test, will be used to evaluate any changes in perceived hearing handicap, and speech understanding resulting from the intervention. These outcomes will be evaluated at baseline (pre-randomization) and at two follow-up time points post-intervention (i.e., after fitting hearing aids). A linear mixed-model approach will be used to analyze outcome data²⁸. This approach will model an overall baseline mean, along with a mean at each follow-up time point. The same model set up will be used for each outcome measure (TFI, HHIA, and QuickSIN). Contrasts between the follow-up mean estimates and baseline mean will indicate the level of benefit given by the treatment.

Usage of and reactions to wearing the hearing aids will be assessed with both qualitative (exit interview) and quantitative (usage via data-logging) measures. Qualitative analyses of exit interview responses will summarize patient experiences using the devices (e.g., comfort level with wearing the hearing aids, as well as comfort with the amplification, whether there was any sense of stigma from wearing hearing aids, etc.), and self-assessment of benefit. These analyses will follow a similar approach to those described for Aim 2 below. Comparison of the interview responses with actual usage data will provide some validation to self-reported compliance.

VA Clinician Interviews

The Principal Investigator (PI) will email approximately 200 VA audiologists via the National Audiology listserv with the following text:

Please do not “reply all.”

Do you fit hearing aids on Veterans with normal hearing thresholds (25dB HL or better) from .25 kHz through 4 kHz for the purposes of improving quality of life with bothersome tinnitus?

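### Does the uncapped non-Veteran fallback undermine the Veteran recruitment rate and the Aim 1 TFI estimate?

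*Combined protocol and SAP*

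**What the plan says.** Scientific Rationale and Significance lists among the pilot's outputs "recruitment rates of Veterans with normal hearing thresholds through 4 kHz and bothersome tinnitus, compliance and acceptability of the procedures with the target population". It says pilot data are needed "to determine if a randomized controlled trial (RCT) is warranted and, if so, how to conduct the study". Preliminary Studies adds: "This study will obtain initial data with this population of Veteran patients to determine the feasibility and acceptability of this approach". Aim 1 concerns amplification "provided to Veterans with bothersome tinnitus and normal hearing thresholds through 4 kHz".

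Study Population (Hearing Aid Study) sets enrolment at about 20, allows up to 40 consents to cover screen failures, says participants will be Veterans, and then adds: "Non-Veterans will be enrolled if necessary to achieve the target number". Recruitment and Screening gives the order of sources. Medical-record searches come first, in three successive forms. The repository of past study participants follows if those searches do not yield enough candidates. On the repository it says "if the data repository is used for recruitment we may recruit non-Veterans", and more generally "if we are unable to recruit a sufficient number of Veterans we will also recruit civilians". Veterans are named there as the main recruitment focus.

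The Statistical Analysis section for the hearing aid study says: "The primary goal of Aim 1 will be to provide a preliminary evaluation of benefit of low-gain amplification for all participants". It specifies a linear mixed model with one baseline mean and one mean per follow-up, and no term for Veteran status. Neither this section, the outcome measures nor the step-by-step guidance defines a recruitment rate.

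**The concern.** This is a feasibility study, so a recruitment figure is one of its main products and a later trial would be planned on it. The plan gives that figure no numerator, denominator, time unit or breakdown by source. The fallback comes into play when Veterans prove hard to recruit, which is the situation a later trial most needs to know about. With no limit on non-Veterans, a full sample of 20 could hide a Veteran shortfall.

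The second worry is the target population. Aim 1 is about Veterans, but the only planned TFI estimate pools everyone. If non-Veterans responded differently, that estimate would describe a mixed group. At stake are an over-optimistic accrual assumption for the next trial and a TFI change attributed to the wrong population.

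**Working it through.** **Inputs.** From the protocol: about 20 enrolled and up to 40 consented (Study Population), and a 13-point TFI reduction as meaningful to an individual (Outcome Measures). The target of 20 has no SD, power or precision goal behind it, so there is no calculation to reproduce. Assumed, because the documents give no figures: k non-Veterans among 20; a difference d of 5 to 13 points in mean TFI change between non-Veterans and Veterans; an SD of change of 15 to 25; 12 months of recruitment. The Project Timeline table has a recruitment row, but its cell marks were lost in the text, so the planned window cannot be read.

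**1. Which rate is promised.** The rationale promises rates of Veterans. Total enrolment is a different quantity, and no section says it will stand in for the Veteran figure.

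**2. Whether the counts can be recovered.**
- *Veterans enrolled.* Protected Health Information has staff check for, or create, a VA medical record for each subject. Costs To Subjects treats Veterans and non-Veterans separately. Veteran status of enrolled participants should therefore be known.
- *Letters.* The record searches draw on Veterans and VA clinic patients, so these mailings have a Veteran denominator.
- *Consents and screen failures.* Consent is documented, and candidates who fail at the assessment visit are paid, so both leave a trace.
- *Telephone screens.* The exposed counts are these, together with the Veteran status of advertisement responders and repository contacts who never enrol. The guidance refers to a screening script that is not in the public file. Whether it records status and source is unknown, so no omission is shown.

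**3. Size if total enrolment were misread as Veteran enrolment.** Overstatement = 20/(20 − k) − 1.
- k = 2: 20/18 − 1 = 11%
- k = 6: 20/14 − 1 = 43%
- k = 10: 20/10 − 1 = 100%

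Over 12 months, 20/12 = 1.67 per month against 14/12 = 1.17 per month (exact Poisson 95% CI 0.64 to 1.96). The interval for 14 Veterans contains 1.67, so even that contrast is weak.

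**4. Size for the TFI.** Pooled mean minus Veteran mean = (k/20) × d.

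| k | d = 5 | d = 13 |
|---|---|---|
| 2 | 0.5 | 1.3 |
| 6 | 1.5 | 3.9 |
| 10 | 2.5 | 6.5 |

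The 95% half-width for a mean change is t(0.975, n − 1) × SD/√n. At n = 20 it is 0.468 SD, or 7.0 to 11.7 points. Every entry in the table is smaller. The ordering can reverse only with more non-Veterans: at k = 15 and d = 13 the shift is 9.75, which exceeds 7.0 but not 11.7.

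**5. What a Veteran-only estimate would offer.** With 14 Veterans the half-width is 0.577 SD, or 8.7 to 14.4 points, about 23% wider than with 20 (0.577/0.468 = 1.23). It uses data already collected and the same model, so nothing is lost if it is not specified in advance.

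**6. What fixing a split by route would offer.** As an illustration, 14 Veterans from 200 letters is 7.0% (exact 95% CI 3.9 to 11.5%). Divided evenly over three routes, that is about 5 of 67 each: 7.5% (2.5 to 16.6%). The route figures would be too imprecise to separate.

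**The case for a change.** The best case for acting is that descriptive feasibility figures are the product of a pilot with no hypothesis, so they deserve a definition. Some denominators also cannot be rebuilt afterwards. If nobody notes Veteran status and source when an advertisement responder or repository contact first calls, that count is lost. Community advertising is listed in the step-by-step guidance with no trigger, so non-Veterans could enter the screening pool early. The cost of prevention would be at most two screening items and a log.

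Part of this stands. The rate is undefined, the fallback has no numerical limit, and the public text does not say those particular counts are kept. But the loss depends on the content of a script that is not available, and it touches only people who never enrol. The letter-based yield and the number of Veterans enrolled are not affected. A logging item would not supply a cap or a trigger either, and having to use the fallback would itself be informative about Veteran recruitment.

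On the TFI, the objection is weaker. No reason is given why TFI change should differ by Veteran status. The 13-point upper value is a threshold for one person's change, used here only as a generous bound on a difference between groups.

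**Conclusion.** No change is called for. The description of the text is accurate: the Veteran rate is promised without a definition, non-Veterans may fill the target without a cap, and one pooled TFI model is planned. This is missing reporting detail that analysts can supply sensibly, by counting Veterans when reporting a Veteran rate and saying how many non-Veterans were enrolled. No stated rule produces a wrong result.

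The overstatement of 11% to 100% arises only from a misreport the protocol does not plan. The TFI departure of 0.5 to 6.5 points, with up to 10 non-Veterans of 20, lies within the pooled half-width of 7.0 to 11.7 points, and no bias is shown. These sizes rest on assumed splits, group differences and SDs. The conclusion also rests on Veteran status being recoverable for enrolled participants, which the records provisions support but do not state outright. A sample made up mostly of non-Veterans would weaken the TFI part; the rules permit it, but the protocol treats non-Veterans as a fallback.
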